218 hyperglycemia. GLP1-RAs decrease post-prandial glycemic excursions and complement  
219 basal-insulin therapy by enhancing endogenous insulin responses in a glucose-dependent  
220 manner, inhibiting glucagon secretion, slowing gastric emptying and promoting satiety. This  
221 combination has been shown to provide better glycemic control, less hypoglycemia, less weight  
222 gain, and reduce glycemic variability compared to basal bolus therapy or GLP1-RA  
223 alone. IDegLira is a novel fixed-ratio combination of degludec 100 u/ml and liraglutide  
224 3.6 mg in a pre-filled pen. IDegLira has been shown to improve glycemic control, with lower risk  
225 of hypoglycemia, less weight gain, and better patient satisfaction compared to basal-bolus or  
226 stepped-up basal therapy. Pharmacokinetics studies showed that IDegLira provided  
227 coverage over the 24-hours interval at steady levels. In the recent DUAL V trial, IDegLira  
228 resulted in greater HbA1c reduction, weight loss and less hypoglycaemia, compared to up-  
229 titration of insulin glargine in patients with T2D with HbA1c 7-10%. More recently in the DUAL  
230 VII trial, patients with HgA1c 7-10% randomize to IDegLira had similar HbA1c reduction, but  
231 with an 89% reduction in the rate of severe or confirmed symptomatic hypoglycemia and weight  
232 loss compared to basal-bolus insulin. Thus, IDegLira is an attractive and option for patients  
233 with severe hyperglycemia, due to potent HbA1c reduction, lower hypoglycemic risk, and  
234 flexibility of once-daily administration, compared to up to five injections per day in basal-bolus  
235 regimen. However, no previous studies have compared the efficacy and safety of IDegLira in  
236 patients with high HbA1c >9-15%.

237

238

239 **SIGNIFICANCE AND INNOVATION:**

240                   The proposed study will test three innovative questions in patients with poorly controlled  
241                   T2D and HbA1c  $\geq 9\%$ : 1) whether IDegLira, a novel FRC of degludec and liraglutide, results in  
242                   similar glycemic control, 2) less hypoglycemia, less glycemic variability and less weight gain  
243                   compared to a basal-bolus, and 3) whether IDegLira results in better patient satisfaction and  

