509 disease) or significantly impaired renal function (GFR  $<$  30 ml/min).  
510 10. Treatment with oral or injectable corticosteroid (equivalent or higher than prednisone 5  
511 mg/day), parenteral nutrition and immunosuppressive treatment.  
512 11. Mental condition rendering the subject unable to understand the nature, scope, and possible

513           consequences of the study  
514   12. Hypersensitivity to study drugs  
515   13. Participating in another investigational drug trial  
516   14. The receipt of any investigational drug (within 3 months) prior to this trial.  
517   14. Previously randomized in this trial  
518   15. Heart Failure NYHA class 4 or uncontrolled hypertension (blood pressure > 180/110  
519           mmHg)  
520   16. Female subjects who are pregnant or breast-feeding at time of enrollment into the study  
521   17. Females of childbearing potential who are not using adequate contraceptive methods (as  
522           required by local law or practice)  
523   18. Known or suspected allergy to trial medications (degludec, liraglutide, aspart), excipients, or  
524           related products.  
525   19. Subjects could be excluded based on PI's discretion  
526   20. Unable to comply with trial protocol, and/or at investigator discretion  
527   21. Patients receiving treatment for active diabetic retinopathy or with proliferative retinopathy

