672 Metformin dose will be titrated up to 1000mg twice daily or to the maximum tolerated  
673 dose, unless contraindicated, per investigator's discretion.
- 674 • Basal Insulin therapy [NPH, mixed insulin, or basal insulin (glargine U100, detemir)] at  
675 TDD ≤50 units will continue at same insulin dosage until randomization. Insulin can be  
676 initiated, or dose could be increased during run-in period in those subjects with severe  
677 hyperglycemia (BG>300 mg/dL) and/or glucotoxicity per investigator's discretion, for  
678 subject's safety reasons.
- 679 • Patients will be instructed in performing glucose testing at home before meals, with a  
680 minimum of 2 out of the 4 pre-meal and/or bedtime glucose measurements per day.
- 681 • Patient not randomized in the trial will be considered screening failures, and no data will  
682 be collected since these patients will not receive study medication.

683

684

685

686 Preparation for Visit 2 (Randomization visit)

- 687 • Patient will be instructed to complete the 8-point SMBG, and to titrate up metformin,  
688 unless contraindicated.
- 689 • All patients will be instructed to provide daily glucose records. In addition, they will

690                   perform an 8-point SMBG done prior to Visit 3 (as described above).

691     • Patients who complied with the 8-point glucose testing (up to 6 points) and fulfill the

692                   eligibility criteria at Visit 2 will be randomized to participate in the study.

693     • Reminder to bring CGM sensor for collect and download.

694

695

696     **Randomization (Visit 2, Week 0)**

697     • Patients will be randomized to each treatment group

698     • Continue metformin therapy at same dose, unless contraindicated or for safety issues

699     • Discontinue other OADs and insulin formulation

700     • If BG > 400 mg/dl, patients will not be randomized, and considered screening failures.

701     • If BG > 300 mg/dl, investigator may order a confirmatory glucose test (at a different time)

702                   before considering the subject screen failure.

703     • Subjects will receive detailed instruction on the use of the IDegLira pen or IDeg and

704                   Aspart Pens and the titration algorithm.

705     • Patient will receive study medications. Subjects randomized to IDegLira will be

706                   instructed to not exceed 50 dose steps and to notify investigators if needed.

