## 909 **Interim Analysis**

910

911 We plan to perform interim analysis on the primary safety endpoint every 6 months. The  
912 trial will be stopped if there is evidence beyond a reasonable doubt of a difference in the rate of  
913 death (two-sided alpha level, <0.01) between the treatment groups. In addition, the trial will be  
914 stopped if the rate of severe hypoglycemic events (BG <40 mg/dl) in either group is > 40%.

915 **Explorative Statistical Analysis for Pharmacogenetics and Biomarkers**

916 N/A

917 **DATA HANDLING AND RECORD KEEPING:**

918 Data collection records with personal identifiers will be stored in locked file cabinets.  
919 Sponsor site expects data to be entered in REDCap within 10 days of phone call or outpatient  
920 visit. The study coordinators will enter data from each visit into data collection paper forms and  
921 into an electronic database (REDCap) that meets HIPPA and confidentiality regulations,  
922 provided by the Emory Research Information Technology Department. Baseline data will include  
923 demographics/history form (subject's gender, date of birth, ethnicity, history of diabetes, and  
924 treatment of diabetes and comorbid conditions, body weight, BMI. During follow-up visits, data  
925 from SMBG, laboratory and/or CGM will be also collected. Data on adverse events will also be  
926 collected and enter into the database. Presentation of the study results at regional or scientific  
927 meetings or in publications will not identify subjects. Access to research and confidential  
928 records will be limited to clinical investigators, research coordinators, and the IRB at Emory  
929 University.

930

931 **ETHICS:**

932 **Informed Consent.**

933 After identification of eligible patients these individuals will be provided basic information  
934 regarding the study and, if interested, a member of the research staff using inclusion/exclusion  
935 criteria delineated elsewhere in the protocol will enroll patients. Informed consent will be  
936 obtained before any trial related procedures including screening procedures. The consent form,  
937 potential risks and benefits, and the rights of research participants will be explained to the  
938 participant by the investigators or research coordinator. Individuals will be asked if they have  
939 questions, and a member of the research staff will answer questions. The principal investigator

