940 will also be available at all times to answer questions that participants may have during the  
941 consent procedure or during the time a participant is enrolled in the study. The consent form  
942 will be completed in accordance with the IRB guidelines of Emory University. A signed copy of  
943 the consent form will be provided to the participant and a copy will be placed in the file that is  
944 maintained for each participant in the study office.

945 Informed consent will follow the procedure of Emory University Institutional Review  
946 Board. Every potential participant will be informed in writing and verbally with the important and  
947 key points of the study. One of the investigators or research coordinators will obtain an  
948 informed consent prior to inclusion of a patient into the study.

949 The study will be conducted in accordance with the Declaration of Helsinki and will be  
950 conducted in accordance with the ICH GCP guidelines. The sponsor-investigator will comply  
951 with all applicable regulatory and legal requirements, ICH GCP guidelines and the Declaration  
952 of Helsinki in obtaining and documenting the informed consent.

953

954 **STUDY SCHEDULE:**

955 The study will be conducted at two sites: at 1) Emory University Hospital Midtown and  
956 Grady Memorial Hospital in Atlanta, GA; and at 2) TBA. An additional site will be considered if  
957 funds are available.

958 Based on our prior trials experience, we anticipate 3-4 potential candidates per week,  
959 including the collaborating institutions, for a total recruitment period of approximately 12  
960 months. Since the study requires a 6-month follow up period, we anticipate a study length of  
961 18-24 months.

First subject in	2019 January
Screening	~300
Randomized	150
Last subject recruited	2020 June/July
Last subject in (completed)	2021 Nov/Dec
Data analysis	2021 DEC
Submission to congress or journal	ADA 2021, Major journal and/or Diabetes Care 2021

962

963 **Study DRUGS and materials:**

964 **Study medication(s) / devices(s)**

965 • Group 1: IDegLira pens will be supplied by the sponsor and given free of charge to the study  
966 subjects. IDegLira is a FRC agent, including basal insulin degludec and GLP-1 agonist

967 liraglutide. The starting dose of IDegLira is at 16 dose steps (degludec 16 units/liraglutide  
968 0.6 mg). The maximum allowed dose of IDegLira 50 dose steps provide 50 U of  
969 degludec and 1.8mg of liraglutide.

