### 980 **Storage and Drug Accountability of Study Medication(s)**

981 Emory and Grady Investigational Drug Service, is a full-service research pharmacy with  
982 all required conditions for proper storage and dispensing of study medications. The investigator  
983 will ensure the availability of proper storage conditions and record and evaluate the temperature.  
984 There will be no trial medication(s) dispensed to any person not enrolled in the study. Any  
985 unused medication(s) will be stored separately from used trial medication(s). Subject  
986 compliance will be assessed by asking subjects to return all unused, partly used and unused  
987 cartridges and vials of liraglutide and degludec insulin at each visit. Subjects will be instructed to  
988 return all used, partially used or unused study products before each dispensing visit. Subjects  
989 will be encouraged at every visit to adhere to the study medications and follow-up schedule. Any  
990 partially used or unused study medications will be destroyed accordingly to local procedures.  
991 After study completion, any surplus of study medications or supplies will be disposed as per local  
992 regulations.

993

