### 997 **Randomization and Blinding**

998 This is an open label randomized controlled trial. Patients will be randomized  
999 consecutively using a computer-generated randomization table provided by [name],  
1000 Professor of Statistics at the Emory School of Public Health. Patient will be randomized based  
1001 on HbA1c (HbA1c <10 or ≥10). The randomization table will be mailed to each institution where

1002 a member of the research team will be in charge of the randomization process and group  
1003 assignment.

1004 **Breaking of Blinded Codes**

1005 N/A

1006

1007

1008 **CONCOMITANT ILLNESSES AND MEDICATIONS:**

1009 **Definitions:**

1010 Concomitant illness: any illness that is present at the start of the trial (*i.e. at the first visit*).

1011 Concomitant medication: any medication other than the trial product(s) that is taken during the  
1012 trial, including the screening and run-in periods.

1013 Details of all concomitant illnesses and medication must be recorded at trial entry (*i.e. at the first*  
1014 *visit*). Any changes in concomitant medication must be recorded at each visit. If the change  
1015 influences the subject's eligibility to continue in the trial, the sponsor must be informed.

1016 The information collected for each concomitant medication includes, at a minimum, start date,  
1017 stop date or continuing, and indication.

1018 For each concomitant illness, date of onset, date of resolution or continuing, at a minimum,  
1019 should be recorded.

1020

1021 **ADVERSE EVENTS:**

1022 The investigator will be responsible for reporting of all adverse events including serious  
1023 adverse events (SAE), serious adverse drug reactions (SADRs) to the competent authority and  
1024 independent IRB boards based upon federal regulations and local/IRB policies. The investigator  
1025 will report to the sponsor all S A R D s at the same time it's reported to the IRB or within 15  
1026 days of the investigator becoming aware.

1027 The investigators will collect the following information at minimum for each of these events:

1028 1. Study name

1030 2. Patient identification (e.g. initials, sex, age)

1031 3. Diagnosis

1032 4. Drug

1033 5. Reporter identification (e.g. Name, or initials)

1034 1035 Also 6) Causality, and 7) Outcome might be reported, but this is not mandatory.

1036

1037

1038

1039

1040 **Definitions**

1041 **Adverse Event (AE):**

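### The randomisation table is mailed to the sites and run by a research-team member in an open-label trial, with no allocation concealment and no separation from recruiters stated

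*Combined protocol and SAP*

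**What the plan says.** Randomization and Blinding is the only description of allocation. The trial is open-label. Patients are randomised consecutively from a computer-generated table supplied by a university statistician, by HbA1c below 10 or at least 10. On custody it says "The randomization table will be mailed to each institution where" "a member of the research team will be in charge of the randomization process and group" assignment.

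Enrolment is described under Ethics, Informed Consent: people are given basic information "regarding the study and, if interested, a member of the research staff using inclusion/exclusion" criteria enrols them. The protocol does not say whether this is the person who holds the table.

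The section Randomization (Visit 2, Week 0) says only that patients will be randomised to a group. The drug packaging and storage sections give the Investigational Drug Service packing, labelling, storage and dispensing duties, but no part in allocation. The protocol mentions no sealed envelopes, no central, web or telephone release, no restricted access to the list, and no recording of eligibility before assignment.

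**The concern.** If the people who decide on entry can see the list, they can know what the next patient will receive. Open-label treatment makes this matter more, because every line on the list has a known meaning. The regimens also differ in burden: the background section cites for IDegLira the "flexibility of once-daily administration, compared to up to five injections per day in basal-bolus" treatment. Staff may reasonably hold views on which patient suits which arm, and no bad faith is needed for those views to affect who is entered.

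Selective entry would make the arms differ before treatment starts, in both HbA1c change and hypoglycaemia. Depending on direction, the result is a false non-inferiority claim or lost power. Measured factors such as baseline HbA1c can be adjusted for. Unmeasured ones, such as expected adherence, cannot.

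**Working it through.** **1. Is there room to steer entry?**

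Rules that limit it:
- Patients are randomised consecutively (Randomization and Blinding).
- A glucose above 400 mg/dl bars randomisation (Visit 2).
- Visit 2 has a window of ±3 days (Table 1).

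Rules that leave room:
- Exclusion Criteria, item 19: "Subjects could be excluded based on" the principal investigator's discretion, with no criteria given.
- Visit 2, glucose above 300 mg/dl: the "investigator may order a confirmatory glucose test (at a different time") before calling a screen failure, so the repeat test is optional.
- Table 1 has eligibility checked again at Visit 2, the randomisation visit.
- About 300 are to be screened for 150 randomised, so non-entry will be common. The run-in instructions say no data are collected on patients who are not randomised, so selective non-entry would be hard to detect later.

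Consecutive randomisation fixes the order of assignments. It does not fix who is entered next.

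**2. The plan's own sample size.**

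Inputs from Sample Size Calculation: SD 0.85, margin 0.4, true difference 0, one-sided alpha 0.05, two-sample t-test, 57 per arm, 20% attrition, 75 per arm recruited.

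- Standard error = 0.85 × √(2/57) = 0.159.
- Non-centrality = 0.4/0.159 = 2.51 on 112 df.
- Power = 80.3%, which reproduces the stated 80%.
- Evaluable after attrition: 75 × 0.8 = 60 per arm. Standard error = 0.85 × √(2/60) = 0.155; df 118; power 82.1%.

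**3. From steering to bias (assumed, not in the documents).**

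Let f be the share of all 150 entrants who are steered, and D the amount by which their expected HbA1c change differs from that of the patients they displace. With 75 per arm and all steering working in one direction:

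net bias b = 2 × f × D

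Example: f = 10% is 15 patients. If all are in one arm, b = 15/75 × 1.0 = 0.2. If they are split evenly between the arms with opposite effect, b = 7.5/75 + 7.5/75 = 0.2 again. Attrition is taken as unrelated to steering.

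| f | b if D = 1.0 | b if D = 0.5 |
|---|---|---|
| 2.5% | 0.05 | 0.025 |
| 5% | 0.1 | 0.05 |
| 10% | 0.2 | 0.1 |

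**4. From bias to error rates.**

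Non-central t, 60 per arm, df 118. False non-inferiority (true difference 0.4, bias favouring IDegLira) uses non-centrality b/0.155. Power (true difference 0, bias against IDegLira) uses (0.4 − b)/0.155.

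| b | False non-inferiority | Power |
|---|---|---|
| 0 | 5.0% | 82.1% |
| 0.025 | 6.9% | 77.6% |
| 0.05 | 9.3% | 72.5% |
| 0.1 | 15.8% | 60.9% |
| 0.2 | 35.8% | 35.8% |

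The last row agrees across columns because 0.2 is half the margin. Bias against IDegLira lowers the false-claim rate: 1.1% at b = 0.1 and 0.2% at b = 0.2. The number analysed matters little: at b = 0.1, false non-inferiority is 15.4% with 57 per arm and 17.7% with 75.

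**The case against.** The strongest reply is that the protocol is silent; it does not describe an open list. It puts one team member in charge, which is compatible with a custodian who never recruits. That is fair, and nothing here shows that recruiters will see the table. But the plan does state a procedure, and following it as written would allow them to.

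Second, consent and screening take place at week −2 and assignment at week 0. With 3–4 candidates a week and two HbA1c strata, whoever consents a patient could not reliably match that patient to a known slot. Holding a patient back at Visit 2 would usually lose a recruit. This lowers the risk, but discretion at Visit 2 remains.

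Third, the larger figures rest on D = 1.0 point, about 1.2 times the planned SD (1.0/0.85), with every steered patient pushing the same way. Stratification also limits imbalance in baseline HbA1c. These points stand, and the large-bias rows should not drive the judgement.

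Fourth, five injections a day is a maximum from the background section. The aspart instructions allow a start with one mealtime dose at the investigator's discretion, so the contrast at entry can be smaller.

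Two defences do not hold. Concealment before assignment is possible without blinding afterwards. And a laboratory HbA1c, which Rationale for study design relies on, limits assessment bias but not selection at entry.

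**Conclusion.** The concern holds. It rests on the stated custody of the table, the absence of any concealment step or separation of roles, and the remaining discretion at Visit 2. It does not depend on the illustrated numbers.

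The size and direction of any bias are unknown. On the assumed values, the effect runs from slight (b = 0.025) to serious (b = 0.2). A bias of 0.1, a quarter of the margin, already about triples the 5% error rate. The two-sample tests that Statistical Methods puts first would not correct for it, and later modelling reaches only measured traits.

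This should be changed. Confidence is medium, because a site procedure outside these documents may already conceal allocation.

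**What to change.** Replace the mailed site table with concealed allocation, and state in Randomization and Blinding:

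- The list, stratified by HbA1c below 10 or at least 10, is held centrally (by the statistician's office, or in REDCap if its randomisation function is available), or by a pharmacy or other person with no part in recruitment.
- The holder's role is named, with a statement that this person does not recruit.
- Each assignment is released singly, after consent, eligibility and baseline data are recorded for that participant.
- Any block sizes are kept from site staff.

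A paper list would still serve if its holder is outside recruitment and these release rules apply.

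The cost is modest set-up work and a short protocol change, with no added patients or procedures. Two points need confirming. The pharmacy route is documented only for the first site ("Emory and Grady Investigational Drug Service, is a full-service research pharmacy with" the required storage and dispensing conditions), while Study Schedule still lists the sites as Emory University Hospital Midtown and "Grady Memorial Hospital in Atlanta, GA; and at 2) TBA", so the second site needs its own arrangement. REDCap is described only for data entry, so its randomisation function must be checked.

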**1152           Precautions/Over-dosage**

1153           We will follow safeguards to minimize the risk to our subjects: a) we will carefully monitor  
1154 capillary blood glucose and reported symptoms. To minimize significant clinical events, we will  
1155 exclude patients with history of significant liver, renal or cardiac failure in this study.

1156

1157           Hypoglycemia can occur during the treatment with insulin. Hypoglycemia will be treated  
1158 accordingly to the best local practices, and insulin will be adjusted as per a predefined  
1159 algorithm. Subjects will be instructed to not exceed the maximum dose of IDegLira of 50  
1160 steps. Subjects will be instructed to maintain good hydration, and to report the presence of  
1161 severe nausea, vomiting, or diarrhea. Insulin doses will be adjusted for hypoglycemic values.

1162

1163

